8. CHANGES TO ANALYSES SPECIFIED IN THE PROTOCOL

The following items were changed between the final version of the protocol and the final SAP.

- Primary efficacy endpoint analyses were modified per FDA feedback.
- Due to the distribution of the data, current use of statins or other lipid-modifying therapies at baseline (yes or no) was removed from the primary analyses and included as factors in the models of the sensitivity analyses.
- Imputation methods were modified per FDA feedback.
- Subgroup analyses were added for select variables.
- A secondary efficacy endpoint was renamed from mean maximum percent change to maximum percent change.
- The exploratory endpoint, proportion of subjects in each group with any LDL-C reduction from baseline at any visit (responders), was added
- Identification of PCS/CS laboratory values were modified.

APPENDIX 1. DETAILS OF MMRM USED FOR EFFICACY ANALYSES

A number of efficacy analyses will utilize a mixed-effects model for repeated measures (MMRM). This includes the co-primary efficacy endpoints (in the case of the first co-primary efficacy endpoint, it will be used as a sensitivity analysis), the key secondary efficacy endpoints, and other secondary efficacy endpoints.

The models will generally include fixed effects for treatment, visit, baseline value, and the interaction between treatment and visit. The current use of statins or other lipid-modifying therapies will also be included as a fixed effect for some sensitivity analyses. The visits will include Days 90, 150, 270, 330, 450, and 510, with Day 510 as the primary time-point. Linear combinations of the estimated means will be created for the various hypothesis tests. Note that for time adjusted percentage change analyses (second co-primary efficacy endpoint) Day 90 will be excluded from the models.

The Restricted Maximum Likelihood (REML) estimation approach will be used with the covariance structure set as "Unstructured." The least squares means will be calculated for each treatment at each visit.

The analysis will be carried out using the SAS PROC MIXED procedure.

Sample SAS statements follow:

```
ods output LSmeans=estimates;
ods output Diffs=lsdiffs;
Proc Mixed Data=ldl_data;
   Class treatment visit_day subject_id;
   Model percent_change = treatment|visit_day base_value/DDFM=KR;
repeated visit_day/type=UN subject=subject_id;
LSMeans treatment*visit_day/cl pdiff=control('0' '510');
run;

(where ('0' '510') is the value of the placebo ['0'] at day 510 ['510'] in interaction term treatment*visit_day)
```

APPENDIX 2. MULTIPLE IMPUTATION WASHOUT MODEL

A multiple imputation washout model will be utilized for the primary efficacy analysis of the percentage change in LDL-C from baseline to Day 510 endpoint. The washout model can be thought of as a modified control-based Pattern-Mixture Model (PMM) that will be used to explore the possibility of data missing not at random (MNAR) for subjects who discontinued the study early. For subjects who discontinued the study early, their missing values will be imputed under the assumption that their outcome would be similar to those in the placebo group with similar background characteristics. For subjects in the inclisiran group only missing Day 510 values will be imputed. For subjects in the placebo group their missing values over all visits after early termination will be imputed based on the missing at random (MAR) assumption. Multiple imputation will be used to account for uncertainty in the imputation process and results from the imputed datasets will be combined using Rubin's method. Further details are provided below.

Windowing will be performed first (see Section 6.3.3) and any missing data will be imputed using the following steps.

The covariates and baseline characteristics which can be predictive of the response for the subjects in the inclisiran group who completed all 4 doses and have data present at Day 540 (considered to have completed the study) will be included in a multiple imputation procedure (SAS PROC MI) and will include the following:

- Baseline value of efficacy measurement (continuous)
- Observed value of efficacy measurement at Day 510 from the inclisiran group (continuous)
- Current use of statins or other lipid-modifying therapies (categorical)

The covariates and baseline characteristics which can be predictive of the response for the remaining subjects in the inclisiran group will be included in a multiple imputation procedure (SAS PROC MI) and will include the following:

- Baseline value of efficacy measurement (continuous)
- Observed value of efficacy measurement at Day 510 from the placebo group (continuous)
- Current use of statins or other lipid-modifying therapies (categorical)

The covariates and baseline characteristics which can be predictive of the response for the placebo group will be included in a multiple imputation procedure (SAS PROC MI) and will include the following:

- Baseline value of efficacy measurement (continuous)
- Observed value of efficacy measurement at Day 90 (continuous)
- Observed value of efficacy measurement at Day 150 (continuous)
- Observed value of efficacy measurement at Day 270 (continuous)
- Observed value of efficacy measurement at Day 330 (continuous)
- Observed value of efficacy measurement at Day 450 (continuous)

- Observed value of efficacy measurement at Day 510 (continuous)
- Observed value of efficacy measurement at Day 540 (continuous)
- Current use of statins or other lipid-modifying therapies (categorical)
- 1. Intermittent missing data in the placebo treatment group will be imputed using MCMC methods, assuming MAR. SAS PROC MI will be utilized for this step using the MCMC impute=monotone option. A total of 100 datasets will be created. These datasets will be utilized in Step #2.
- 2. The remaining missing values in the placebo group with a monotone missing data pattern will be imputed in this step. Missing data will be imputed assuming data are MAR. Only subjects in the placebo group will be utilized in this step. SAS PROC MI will be used to impute missing values utilizing the monotone reg option. This will be performed for the 100 datasets. After this step, the 100 datasets will be fully imputed for the placebo treatment group. These datasets will be utilized in Step #3.
- 3. Subjects in the inclisiran group who received all 4 doses of study medication, have the Day 510 value missing, and have evaluable data at Day 540 will be included in this step. Missing values at Day 510 will be imputed assuming data are MAR. Only subjects in the inclisiran group will be included in this step. Observed Baseline and Day 510 data will be utilized to impute missing Day 510 data utilizing SAS PROC MI. This will be performed 100 times to create 100 datasets that are fully imputed at Day 510.
- 4. The remaining missing values at Day 510 in the inclisiran group will be imputed in this step. Note that the subjects with imputed inclisiran Day 510 data from Step #3 will not be utilized in this step. Control-based PMM imputation will be performed. With this imputation model, the missing efficacy measurements in the inclisiran group will not be constructed from the observed data in the inclisiran group but rather from the observed and imputed data in the placebo group at Day 510. Baseline data will also be utilized in the imputation. The MNAR statement in SAS PROC MI will be used to impute missing values. This will be performed for the 100 datasets.
- 5. The imputed data from Step #3 will be combined with the imputed data from Step #4 to create 100 fully imputed datasets.
- 6. A total of 100 fully imputed datasets will be created (M=100). Since multiple imputation is a stochastic method, slight differences in output can be expected for different initial states of the random number generator. The seed numbers will be identified in the SAS programs to allow for reproducibility.
- 7. After the missing data imputation is completed using the above steps, absolute change/percentage change values will be calculated in each of the imputed datasets at each visit.
- 8. These 100 datasets will be analyzed using ANCOVA models with fixed effect of treatment group and baseline LDL-C as a covariate for the percent change of LDL-C from baseline to Day 510 primary efficacy endpoint.

9. Treatment effects (difference in LS means between treatments) from these 100 analyses will then be combined using Rubin's Method via SAS PROC MIANALYZE procedure for each endpoint.

APPENDIX 3. CONTROL-BASED PATTERN MIXTURE MODEL

A control-based Pattern-Mixture Model (PMM) will be used to explore the possibility of data missing not at random (MNAR) for subjects who discontinued the study. For subjects who discontinued the study without any further follow-up data, their missing values after study discontinuation will be imputed under the assumption that their outcome would be the similar to those in the placebo group with similar background characteristics. For subjects who did not discontinue the study, their intermittent missing values will be imputed based on the MAR assumption. Multiple imputation will be used to account for uncertainty in the imputation process and results from the imputed datasets will be combined using Rubin's method. Further details are provided below.

Windowing will be performed first (see Section 6.3.3) and any missing data will be imputed using the following steps.

The covariates and baseline characteristics which can be predictive of the response will be included in a multiple imputation procedure (SAS PROC MI) and will include the following:

- Baseline value of efficacy measurement (continuous)
- Observed value of efficacy measurement at Day 90 (continuous)
- Observed value of efficacy measurement at Day 150 (continuous)
- Observed value of efficacy measurement at Day 270 (continuous)
- Observed value of efficacy measurement at Day 330 (continuous)
- Observed value of efficacy measurement at Day 450 (continuous)
- Observed value of efficacy measurement at Day 510 (continuous)
- Observed value of efficacy measurement at Day 540 (continuous)
- Current use of statins or other lipid-modifying therapies (categorical)
- 1. Intermittent missing data will be imputed using MCMC methods, assuming MAR, within each treatment group. SAS PROC MI will be utilized for this step using the MCMC impute=monotone option. A total of 100 datasets will be created. These datasets will be utilized in Step #2.
- 2. The remaining missing values with a monotone missing data pattern will be imputed in this step. Control-based PMM imputation will be performed. With this imputation model, the missing efficacy measurements in the inclisiran group will not be constructed from the observed data in the inclisiran group but rather from the observed data in the placebo group. We will also use this model to impute missing efficacy measurements in the placebo group. The MNAR statement in SAS PROC MI will be used to impute missing values under the aforementioned assumptions. This will be performed for the 100 datasets. After this step, the 100 datasets will be fully imputed.
- 3. A total of 100 fully imputed datasets will be created (M=100). Since multiple imputation is a stochastic method, slight differences in output can be expected for different initial states of the random number generator. The seed numbers will be identified in the SAS programs to allow for reproducibility.

- 4. After the missing data imputation is completed using the above steps, absolute change/percentage change values will be calculated in each of the imputed datasets at each visit.
- 5. These 100 datasets will be analyzed using the MMRM described in Appendix 1 for the coprimary efficacy endpoints and key secondary efficacy endpoints.
- 6. Treatment effects (difference in LS means between treatments) from these 100 analyses will then be combined using Rubin's Method via SAS PROC MIANALYZE procedure for each endpoint.

APPENDIX 4. CRITERIA FOR POTENTIALLY CLINICALLY SIGNIFICANT AND CLINICALLY SIGNIFICANT ABNORMAL LABORATORY TESTS

Hemoglobin A1C criteria is explicitly stated in the table below.

All other criteria are met when both of the following occur:

- Post-baseline values meet the thresholds below
- Baseline values or any previous post-baseline values do not meet the thresholds below

Parameter	Unit	Lower Boundary	Upper Boundary
Hematology			
Hematocrit	%	≤0.8 × LLN	N/A
Hemoglobin	g/dL	≤10 g/dL	N/A
Platelet Count	10^9/ L	≤75*	≥700*
White Blood Cell Count	10^9/L	≤2.8	≥16
Serum Chemistry			1
Alanine Aminotransferase (ALT/SGPT)	U/L	N/A	>1 and $\leq 3 \times ULN$
Alanine Aminotransferase (ALT/SGPT)	U/L	N/A	>3 and $\leq 5 \times ULN*$
Alanine Aminotransferase (ALT/SGPT)	U/L	N/A	$>$ 5 and \leq 10 × ULN*
Alanine Aminotransferase (ALT/SGPT)	U/L	N/A	>10 and <20 × ULN*
Alanine Aminotransferase (ALT/SGPT)	U/L	N/A	>20 × ULN*
Alkaline Phosphatase	U/L	N/A	>2 × ULN*
Aspartate Aminotransferase (AST/SGOT)	U/L	N/A	>1 and ≤3 × ULN
Aspartate Aminotransferase (AST/SGOT)	U/L	N/A	>3 and ≤5 × ULN*
Aspartate Aminotransferase (AST/SGOT)	U/L	N/A	>5 and ≤10 × ULN*
Aspartate Aminotransferase (AST/SGOT)	U/L	N/A	>10 and <20 × ULN*
Aspartate Aminotransferase (AST/SGOT)	U/L	N/A	>20 × ULN*
Creatine Kinase (CK)	U/L	N/A	>1 and ≤3 × ULN
Creatine Kinase (CK)	U/L	N/A	>3 and ≤5 × ULN
Creatine Kinase (CK)	U/L	N/A	>5 × and ≤10 x ULN*
Creatine Kinase (CK)	U/L	N/A	>10 and $\leq 20 \times ULN^*$
Creatine Kinase (CK)	U/L	N/A	>20 × ULN*
Hemoglobin A1C	%	N/A	≥6.5% and ≥0.5% change from baseline
Serum Creatinine	mg/dL	N/A	≥50% increase from Baseline or >2 mg/dL*
Total Bilirubin	mg/dL	N/A	>2 × ULN*

LLN: \underline{L} ower \underline{l} imit of the standard reference (\underline{n} ormal) range; ULN: \underline{U} pper \underline{l} imit of the standard reference (\underline{n} ormal) range; N/A is Not Applicable.

^{*}Clinically significant laboratory boundaries.

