4.2. Inclusion Criteria

Subjects may be included in the study if they meet all of the following criteria:

1. Male or female subjects ≥ 18 years of age.
2. History of HeFH with a diagnosis of HeFH by genetic testing; and/or a documented history of untreated LDL-C of >190 mg/dL, and a family history of FH, elevated cholesterol or early heart disease may indicate FH ([APPENDIX A](#))
3. Stable on a low-fat diet (eg, NCEP)
4. Serum LDL-C ≥ 2.6 mmol/L (≥ 100 mg/dL) at screening
5. Fasting triglyceride <4.52 mmol/L (<400 mg/dL) at screening.
6. Calculated glomerular filtration rate >30 mL/min by estimated glomerular filtration rate (eGFR) using standardized clinical methodology.
7. Subjects on statins should be receiving a maximally tolerated dose. Maximum tolerated dose is defined as the maximum dose of statin that can be taken on a regular basis without intolerable adverse events. Intolerance to any dose of any statin must be documented as historical AEs attributed to the statin in question in the source documentation and on the Medical History page of the electronic case report form (eCRF) (see [APPENDIX B](#)).
8. Subjects not receiving statin must have documented evidence of intolerance to all doses of at least two different statins (see [APPENDIX B](#)).
9. Subjects on lipid-lower therapies (such as a statin and/or ezetimibe) should be on a stable dose for ≥ 30 days before screening with no planned medication or dose change during study participation.
10. Subjects must be willing and able to give informed consent before initiation of any study-related procedures and willing to comply with all required study procedures.

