6.4.8.2. Laboratory Tests

Laboratory values will be summarized by treatment group, including the observed value, changes and percent changes from baseline at each time point.

A shift analysis using the normal range (except for eGFR and HbA1c) will be done which counts the number of subjects with a low, normal or high value at baseline and a low, normal or high value post baseline.

The following ranges will be used for eGFR and HbA1c

- For eGFR, the categories will be Severe = $<30 \text{ mL/min}/1.73\text{m}^2$; Moderate = $\ge 30 \text{ to } <60 \text{ mL/min}/1.73\text{m}^2$; Mild = $\ge 60 \text{ to } <90 \text{ mL/min}/1.73\text{m}^2$; and Normal = $\ge 90 \text{ mL/min}/1.73\text{m}^2$.
- For HbA1c, the categories will be $\leq 5.6\%$, $\geq 5.7\%$ to $\leq 6.4\%$, and $\geq 6.5\%$.

The baseline and worst post-baseline value will be utilized for the shift tables. Note that the shift table dealing with the fasting glucose parameter will require the lab sample to be taken while fasting. Samples taken while the subject was not fasting will not be analyzed.

The number and percentage of subjects with potentially clinically significant (PCS) laboratory values and clinically significant (CS) laboratory values (refer to Appendix 4 for the criteria) will be summarized by treatment group. Hemoglobin A1c criteria is explicitly stated in Appendix 4. All other PCS and CS criteria are met when both of the following occur:

- Post-baseline values meet the thresholds listed in Appendix 4
- Baseline values or any prior post-baseline values do not meet the thresholds listed in Appendix 4

PCS chemistry laboratory values will also be classified as follows:

- Abnormal baseline:
 - Non HbA1c: >1 and \leq 3x ULN at baseline and >1 and \leq 3x ULN at final visit
 - o HbA1c: ≥6.5% at baseline and ≥6.5% and ≥0.5% change from baseline at final visit

• Elevated further:

○ Non HbA1c: >1 and \leq 3x ULN at baseline or post baseline and becoming > 3x ULN post baseline

• Final visit:

- Non HbA1c: >1 and \leq 3x ULN at final visit only but not at baseline or previous visits
- o HbA1c: \geq 6.5% and \geq 0.5% change from baseline at final visit only but not at baseline or previous visits

• Persistently elevated:

- Non HbA1c: >1 and \leq 3x ULN at a post baseline visit and remains >1 and \leq 3x ULN until final visit

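### Read as printed, SAP Appendix 4 cannot flag a creatinine rise of 50% or more in a subject who enters above 2 mg/dL and stays above it

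*SAP*

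**What the plan says.** SAP Appendix 4 lists the boundaries for potentially clinically significant (PCS) and clinically significant (CS) laboratory values. Creatinine has a single row with a single upper boundary, "≥50% increase from Baseline or >2 mg/dL", carrying the asterisk that marks a CS boundary.

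HbA1c is set apart: "Hemoglobin A1C criteria is explicitly stated in the table below". For the other parameters, "All other criteria are met when both of the following occur". The first condition is "Post-baseline values meet the thresholds below"; the second is "Baseline values or any previous post-baseline values do not meet the thresholds below". SAP 6.4.8.2 repeats the rule ("All other PCS and CS criteria are met when both of the following occur") and adds separate listings of subjects with PCS and CS values. Protocol 10.4.4.2 states a simpler form: incidence among subjects with no PCS/CS value at baseline.

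ALT, AST and CK each have several rows, one per grade. Protocol 4.2, criterion 6, requires an eGFR above 30 mL/min; no entry or exclusion criterion caps creatinine. The SAP addendum does not touch the creatinine row.

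**The concern.** The creatinine boundary joins a relative part (a rise from baseline) to an absolute part (a level). A condition that screens out abnormality already present at entry makes sense for the level. It serves no purpose for the rise, because no one can be 50% above their own baseline at baseline. With both parts in one row, a subject who is above 2 mg/dL at entry is screened out of the rise as well.

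The rest of the table suggests this was not intended. HbA1c, the other criterion with a change component, is exempt from the general rule. The graded rows for ALT, AST and CK let a subject who starts elevated still be counted on reaching a higher grade. Creatinine has neither route.

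At stake is the completeness of the renal laboratory table and listing in the subjects with least renal reserve. Renal events are a named safety topic in SAP 6.4.8.1, and Protocol 1.2.2.1 reports that about 25% of the drug is excreted unchanged in urine.

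**Working it through.** The plan states no figure on this point, so there is nothing to reproduce. The check has three steps.

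**1. The logic.** Let b be baseline creatinine and x a later value. The row is met when x ≥ 1.5b or x > 2. Baseline can never meet the first part, and meets the second whenever b > 2. The second condition in Appendix 4 can be read three ways:
- literal: baseline or at least one earlier value does not meet the row;
- strict: neither baseline nor any earlier value meets it;
- protocol: baseline does not meet it.

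| Creatinine series (mg/dL) | One threshold: literal / strict / protocol | Parts tested separately: literal / strict / protocol |
|---|---|---|
| 2.1, 2.5, 3.2, 4.2 | no / no / no | yes / yes / yes |
| 2.1, 4.2, 4.2 | no / no / no | yes / yes / yes |
| 2.1, 1.9, 4.2 | yes / no / no | yes / yes / yes |
| 2.1, 2.1, 2.2, 2.1 | no / no / no | no / no / no |
| 2.0, 4.0 | yes / yes / yes | yes / yes / yes |
| 1.0, 1.5 | yes / yes / yes | yes / yes / yes |

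If every value exceeds 2, every value meets the row, so none of the three readings of the second condition can be satisfied. Separate testing restores the rises and leaves the stable series uncounted.

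**2. Can such a subject enter?** The protocol does not name its eGFR equation. The only formula in the documents is Cockcroft-Gault, in the footnotes to SAP Table 3: (140 − age) × weight / (72 × creatinine), × 0.85 if female. Ages and weights below are assumptions. At 2.1 mg/dL:
- man, 55 years, 85 kg: 85 × 85 / (72 × 2.1) = 7,225 / 151.2 = 47.8 mL/min;
- man, 60 years, 70 kg: 37.0;
- woman, 50 years, 70 kg: 35.4;
- woman, 60 years, 60 kg: 27.0, not eligible.

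The highest creatinine that keeps clearance above 30 runs from about 1.65 mg/dL (woman, 70 years, 60 kg) to 4.63 (man, 40 years, 100 kg). On this formula, entry above 2 mg/dL is possible for many profiles but not all.

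**3. What the eGFR shift table shows.** SAP 6.4.8.2 tabulates baseline against worst post-baseline eGFR with cut-offs at 30, 60 and 90. For the man of 55 years and 85 kg:
- 2.1 to 4.2 (+100%): 7,225 / (72 × 4.2) = 23.9, so 47.8 to 23.9, Moderate to Severe, visible;
- 2.1 to 3.2 (3.2 / 2.1 = 1.52, +52%): 7,225 / (72 × 3.2) = 31.4, so 47.8 to 31.4, Moderate both times, not visible.

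In general, clearance on this formula is inversely proportional to creatinine. A doubling halves it, so any baseline from 30 to under 180 drops at least one category. A rise of exactly 50% multiplies it by 2/3. A subject then stays in Moderate if baseline clearance is 45 to under 60 (45 × 2/3 = 30), while anyone in Mild leaves that category (90 × 2/3 = 60). For the example man the unseen range runs from +50% to about +59% (47.8 / 30 = 1.59).

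**The case against.** The strongest reply is that the gap depends on one reading. Appendix 4 speaks of thresholds in the plural, and the creatinine cell has two parts joined by an or. If the programmers test each part on its own, the rise is always counted and nothing is lost. That stands as a possibility, but the SAP does not say so, and elsewhere in the table separate criteria get separate rows. The literal wording of the second condition would also admit a subject who dips to 2 mg/dL or below and then rises; it does not help one who stays above.

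The next reply is that other outputs cover the case. A reader might infer that a doubling of creatinine would go unseen. The documents do not support that: step 3 shows it in the eGFR shift table, and SAP 6.4.8.2 with 6.3.1 calls for percent change at each time point with its maximum. The acute kidney injury search in Appendix 5 may add cases. What remains is the smaller rise. The percent-change summaries are at group level, and the adverse event search needs a reported event. The Elevated further class in SAP 6.4.8.2 is no clear rescue: it works in multiples of the upper limit of normal (ULN), and creatinine has no such boundary in Appendix 4. If it were applied, with an assumed ULN of 1.1 to 1.4 mg/dL, 3.2 mg/dL is 2.9 to 2.3 times ULN, short of the 3 needed.

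Limiting incidence to subjects without the abnormality at baseline is a fair treatment-emergent convention. That defends the level part of the row, not the rise.

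**Conclusion.** The point holds as a narrow gap in safety reporting. Applied as printed, the creatinine row leaves a subject who enters and stays above 2 mg/dL out of the PCS/CS table and listing for a rise of 50% or more. Where that rise also stays within one eGFR category, no subject-level flag remains. The conclusion assumes that the row is programmed as one threshold; the clearance figures assume Cockcroft-Gault and the stated age and weight.

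The size cannot be given. One might take 0.5 to 2% of the 482 enrolled and speak of 2 to 10 subjects, but the documents offer no basis for that range. It would also count subjects at risk rather than missed events, which need the rise as well and may be none. The number is probably small.

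Two further inferences do not follow. The rule is identical in both arms, so it gives no ground for claiming a biased safety comparison, and efficacy is untouched. That a small step across 2 mg/dL (1.95 to 2.05, +5%) counts as clinically significant is true of any cut-off, and the fix below does not change it.

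**What to change.** Split the creatinine row in Appendix 4 into (a) an increase of 50% or more from baseline, applied to every subject with a baseline value and with no condition on the baseline level, and (b) a value above 2 mg/dL, under the existing baseline condition. Tabulate and list (a), (b) and either. If the program already tests the parts separately, one sentence saying so is enough.

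The addendum offers a pattern: section 2.3 keeps the Hy's Law count that requires normal baseline values and adds a second count without that requirement. Because the addendum postdates unblinding, a change made now should likewise be shown beside the printed version and labelled as added.

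The cost is one more table row and a small program change. Creatinine is already measured at baseline and at the chemistry visits from Day 90 to Day 540, so no new data are needed. The count may become slightly less favourable.
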